### 7.2 Other Assessments

### 7.2.1 Physical Examinations

A complete physical examination will be conducted at the investigational site at Visit 1. At Visits 2 and 3, a directed physical examination will be performed. Height and weight will be measured at Visit 1 only.

Trial Code: 000103 Date: 28-Jul-2014 E-Protocol Amendment-18395; Ver. 5

> Supersedes: 4 Page 36 of 65

After study drug administration, any new abnormal findings or worsening of an ongoing abnormal condition will be recorded as an AE.

### 7.2.2 Vital Signs

Orthostatic vital signs (supine and standing blood pressure and pulse) will be measured at Visits 1 through 4.

### 7.2.3 Clinical Laboratory Variables

All laboratory measurements will be performed using appropriately validated methods by the study site's local laboratory. All sites should follow their local regulations for sample handling and storage.

Laboratory values will be reported to the investigator and sponsor (or the sponsor's representative) and will be entered into the eCRF database, which will be maintained by a clinical research organization selected by the Sponsor.

Out-of-range values will be described in the reference ranges to be provided by the local laboratory. Investigators will assess all out of range values as being either clinically significant or not clinically significant via the eCRF.

Sites will be specially instructed to review all laboratory results in order to determine if the subject is eligible for study participation, and to determine any AEs post study drug administration.

Samples will be collected during Visits 1, 3 and 4 for determination of the following test values:

- Hematology panel:
  - o Full complete blood count and differential
- Coagulation panel:
  - o Prothrombin time, activated partial thromboplastin time
- Full chemistry panel:
  - o Calculated creatinine clearance
  - o Serum magnesium (Mg++)
  - o Serum chemistry: glucose, blood urea nitrogen, potassium, sodium, chloride, calcium, total protein, albumin, total bilirubin, alkaline phosphatase, aspartate aminotransferase, alanine aminotransferase, bicarbonate and gamma glutamyl transferase
- Urinalysis panel

In addition, urine pregnancy tests will be performed at the local laboratory for female subjects of childbearing potential at Visits 1 and 2.

Trial Code: 000103 Date: 28-Jul-2014

E-Protocol Amendment-18395; Ver. 5

Supersedes: 4 Page 37 of 65

# 7.3 Drug Concentration Measurements

For subjects that are participating in the PK subset, blood samples for measurement of picosulfate and magnesium plasma concentrations will be collected from approximately 15 subjects in the 3 Prepopik groups. Magnesium will be collected pre-dose at Visits 1, 2 or 3.). Picosulfate will be collected at Visit 3 (colonoscopy) in the (6-12 hour) window after the first dose of Prepopik. Sampling times at Visit 3 are at Hours 6, 8, and 12 for picosulfate concentrations and at Hour 10 for magnesium concentrations.

Analysis of the samples for sodium picosulfate and magnesium oxide will be performed by

# 7.4 Handling of Biological Samples

Sampling tubes, material for shipment of urine and blood samples, and a laboratory manual detailing all sample collection and shipment procedures will be provided and distributed by the local safety laboratory at each individual trial site. Sampling tubes, material for shipment of PK blood samples, and a laboratory manual detailing all sample collection and shipment procedures will be provided and distributed by the central PK laboratory to all trial sites. The volume of blood withdrawn from subjects is restricted to a minimum to allow evaluation of PK.

Any remaining blood samples not already analyzed for the trial will be stored at the central laboratory until the clinical trial report has been finalized.

Trial Code: 000103 Date: 28-Jul-2014 E-Protocol Amendment-18395; Ver. 5

Supersedes: 4

Page 38 of 65

#### 8 ADVERSE EVENTS

#### **Adverse Event Definition** 8.1

An AE is any untoward medical occurrence in a subject participating in a clinical trial. It includes:

- Any unfavorable and unintended sign, symptom or disease temporally associated with the use of the IMP, whether or not considered to be caused by the IMP
- AEs commonly observed and AEs anticipated based on the pharmacological effect of the IMP
- Any laboratory abnormality, vital sign or finding from physical or gynecological examination assessed as clinically significant by the investigator (note: findings from assessments and examinations done during screening are not AEs, but are recorded as medical history.)
- Accidental injuries, reasons for any change in medication (drug and/or dose), reasons for any medical, nursing or pharmacy consultation, or reasons for admission to hospital or surgical procedures
- Overdoses and medication errors with and without clinical consequences

An adverse drug reaction (ADR) is an AE evaluated by the investigator as being probably or possibly causally related to treatment with the IMP.

A serious ADR is an SAE evaluated by the investigator and/or by Ferring as being probably or possibly causally related to treatment with the IMP (further described in Section 8.2.2).

An unexpected AE is an AE not identified in nature, severity, or frequency in the section "Undesirable Effects" in the sponsor's current Investigator's Brochure and current approved label.

A treatment-emergent AE is any AE that begins during the treatment period, or is a worsening of a pre-existing medical condition. The treatment period is the period during which a subject receives IMP.

#### 8.2 **Collection and Recording of Adverse Events**

#### 8.2.1 **Collection of Adverse Events**

The investigator must monitor the condition of the subject throughout the trial from the time of obtaining informed consent until the last visit.

The sources of AEs cover:

- The subject's response to questions about his/her health (a standard non-leading question such as "How have you been feeling since your last visit?" is asked at each visit).
- Symptoms spontaneously reported by the subject.
- Investigations and examinations where the findings are assessed by the investigator to be clinically significant changes or abnormalities.

Trial Code: 000103 Date: 28-Jul-2014 E-Protocol Amendment-18395; Ver. 5

> Supersedes: 4 Page 39 of 65

• Other information relating to the subject's health becoming known to the investigator (e.g., hospitalization).

# **8.2.2** Recording of Adverse Events

The investigator must record all AEs in the Adverse Event Log provided in each subject's CRF with information about the:

- AE
- Date and time of onset (time can be omitted, if applicable)
- Intensity
- Causal relationship to IMP
- Action taken to IMP
- Other action taken
- Date and time of outcome (time can be omitted, if applicable)
- Outcome
- Seriousness

Each of the items in the Adverse Event Log is described in detail in the following sections.

#### **Adverse Event**

Adverse events should be recorded as diagnoses, if available. If not, separate signs and symptoms should be recorded. One diagnosis/symptom should be entered per record.

If a subject suffers from the same AE more than once and the subject recovers in between the events, the AEs should be recorded separately. If an AE changes in intensity, a worst-case approach should be used when recording the event, i.e., the highest intensity and the longest duration of the event.a

Note the following: A procedure is not an AE; the reason for conducting the procedure is. Hospitalization is not an AE; the reason for hospitalization is. Death is not an AE, but the cause of death is (an exception is sudden death of unknown cause, which is an AE).

-

Exception: if an AE with onset before the first IMP administration (i.e., a pre-treatment AE) changes in intensity, this must be recorded as two separate events. The initial AE should be recorded with outcome "not yet recovered" and the date and time of outcome is when the intensity changed. The second AE should be recorded with date and time of onset when the intensity changed.

Trial Code: 000103 Date: 28-Jul-2014 E-Protocol Amendment-18395; Ver. 5

Supersedes: 4 Page 40 of 65

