# **Intensity**

The intensity of an AE must be classified using the following 3-point scale:

Mild: Awareness of signs or symptoms, but no disruption of usual activity

Moderate: Event sufficient to affect usual activity (disturbing)

Severe: Inability to work or perform usual activities (unacceptable)

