1.1 Definitions/ Abbreviations

Terms	Definitions
Analysis set	Data included in a specific analysis
Aronchick Scale	see Protocol section 7.1
Baseline	The last observed value collected prior to the start of treatment
Change from baseline	Difference between a data value at an analysis time point minus the corresponding baseline value
Concomitant medications	Medication taken during the study
Percent change from	Numerical percent difference between baseline value and post-
baseline	baseline value at a given study visit
Preparation	In this study, this term and the term "treatment," which is generally used in clinical trials, may be used interchangeably
Prior medications	Medications taken before entering the study
Randomization	The unpredictable allocation of a subject to a particular treatment (or preparation) in a clinical trial
Randomized	Subject randomized to trial treatment
Responder	A responder will be defined for the Aronchick Scale as subject rated as excellent or good during the colonoscopy
Screened	Subject who enters Screening
Screening	Questions and assessments performed to determine if a person qualifies to enter a clinical trial
TEAE	Any adverse event that occurs during or after the start of
	treatment or begins prior to preparation and increases in intensity during and/or after the start of preparation

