10.2 Adverse Events

All AEs will be coded using MedDRA version 16.1 or later. The relation between AEs and study medication will be characterized as having a reasonable possibility or not. The intensity of AEs will be characterized as mild, moderate, or severe.

Treatment-emergent AEs are those adverse events which begin after the start of study treatment or which worsen after the start of study medication. Any event with partial date information reported on or after the date of the first dose of study treatment will be considered treatment-emergent. Only treatment-emergent AEs will be summarized.

Written narratives will be issued for all serious AEs (including deaths) and AEs leading to withdrawal.

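### Splitting a pre-treatment adverse event on any change in intensity lets an event that eases after dosing be counted as treatment-emergent

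*Protocol*

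**What the plan says.** **Recording.** The general rule in Protocol 8.2.2 (Adverse Event) is a single record: "If an AE changes in intensity, a worst-case approach should be used when recording the event". A footnote makes an exception for events with onset before the first IMP administration: "i.e., a pre-treatment AE) changes in intensity, this must be recorded as two separate events". The first record is closed with the outcome not yet recovered, and its outcome date and time are those of the change. For the other record, "The second AE should be recorded with date and time of onset when the intensity changed".

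**Classification.** There are three definitions of a treatment-emergent event.

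- Protocol 8.1: "A treatment-emergent AE is any AE that begins during the treatment period, or is a worsening of a pre-existing medical condition". It adds: "The treatment period is the period during which a subject receives IMP".
- SAP 1.1: an event occurring during or after the start of treatment, or one that "begins prior to preparation and increases in intensity during and/or after the start of preparation".
- SAP 10.2: "Treatment-emergent AEs are those adverse events which begin after the start of study treatment or which worsen after the start of study medication".

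**Reporting.** SAP 10.2 restricts the summaries to treatment-emergent events. SAP 10.2.2 tabulates them by term, maximum intensity and relationship, and adds a table of non-serious events with an incidence of at least 5% in any treatment group.

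**The concern.** The exception exists so that a pre-treatment event that gets worse on treatment is visible as such. As worded, it fires on any change of grade. An event that improves is therefore also cut in two, and the improved remainder becomes a separate record with a post-dose onset.

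Each definition has two limbs joined by an 'or'. For an event that began before treatment, the second limb asks for worsening. The split record no longer looks like such an event, so it meets the first limb on its date alone. Neither document tells the programmer to look for a parent record or to compare grades.

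Describing safety is a stated secondary objective, and TEAE incidence is one of its main summaries. In arms of about 15 a single misclassified child is visible in a table.

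**Working it through.** The plan states no adverse event rate, so there is no figure of its own to reproduce here. The check is an enumeration, followed by the effect of one child.

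**Inputs**

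- Grades: mild, moderate, severe (Protocol 8.2.2, Intensity: "The intensity of an AE must be classified using the following 3-point scale").
- Trigger for the split: any change of grade. Onset of the second record: the time of the change (Protocol 8.2.2, footnote).
- Planned group sizes: 15 per arm; 30 for the two 1-sachet arms combined and 30 for the two standard-of-care arms combined; 45 for all Prepopik (Protocol Table 3-1, SAP Table 1).
- Reporting threshold: 5% (SAP 10.2.2).

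**Step 1. Classify the second record.** Take a pre-treatment event still present at the first dose that changes grade afterwards without resolving.

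| Change after first dose | Onset limb of SAP 10.2 met? | Worsening? |
|---|---|---|
| mild to moderate | yes | yes |
| mild to severe | yes | yes |
| moderate to severe | yes | yes |
| moderate to mild | yes | no |
| severe to moderate | yes | no |
| severe to mild | yes | no |

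All six changes meet the onset limb. Only three are the worsening that the definitions require of an earlier event. The other three are improvements counted as emergence.

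**Step 2. Window.** Protocol 8.1 limits onset to the period in which IMP is received, which covers the two doses. SAP 10.2 gives no end to the window, and follow-up runs to Visit 5, 28 (±5) days after colonoscopy. Suppose a child has moderate pain that starts after Visit 2, is still present at the first dose, and eases to mild between the colonoscopy and Visit 4. The second record falls outside the protocol's onset limb but inside the SAP's. The SAP governs the tables, so the wider window applies.

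**Step 3. Effect of one child.** Assume the child has no other treatment-emergent record under that term. The added incidence is 100 × 1/n points. The smallest number of children that reaches 5% is 0.05 × n, rounded up.

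| Group | n | Added by one child | Children needed to reach 5% |
|---|---|---|---|
| One arm | 15 | 100/15 = 6.7 points | 0.75, so 1 |
| 1 sachet combined, or standard of care combined | 30 | 100/30 = 3.3 points | 1.5, so 2 |
| All Prepopik | 45 | 100/45 = 2.2 points | 2.25, so 3 |

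The ½-sachet group has only 15 children in total, so one child is enough there on any reading of 'treatment group'. For 1 sachet and standard of care, one child is enough only if the threshold is applied within age group.

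**The case against.** The strongest reply is that the intent is plain. All three definitions ask for worsening or an increase when the event began before treatment, and no sentence says that an improved remainder counts. A careful programmer might exclude it, and the table shells, which are in a separate document, may already do so. This stands as far as intent goes. It does not settle the handling: the onset limb is sufficient by itself, and the footnote expressly gives the second record its own onset despite the general rule that onset is when symptoms were first noted.

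Second, the affected pool is narrow. This stands. Findings from assessments and examinations at screening are medical history (Protocol 8.1), and Visits 1 and 2 may be combined. The event must start before the first dose without being a screening finding, be moderate or severe, persist at dosing, and then drop a grade without resolving; full recovery is an outcome, not a change of intensity. The protocol also names vomiting, diarrhea, nausea and abdominal pain as the commonest reactions to the product, so for those symptoms easing after dosing is not the obvious direction.

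Third, the information is not lost. This also stands. The parent's outcome date and time equal the second record's onset, intensity is a required field, and all events are listed. The tables by relationship have some protection too, because causality is judged for each record.

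A reader might infer that TEAE rates will be materially inflated in every arm and that differences between Prepopik and standard of care will shrink. The documents do not support this. They give no rate of pre-treatment events and no rate of easing, so neither the inflation nor any dilution can be estimated.

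**Conclusion.** The point holds as a conflict between the recording rule and the intended TEAE definition. Followed literally, Protocol 8.2.2 and SAP 10.2 count a pre-treatment event that eases after dosing, without resolving, as treatment-emergent. Protocol 8.1 and SAP 1.1 show that this is not what was meant.

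The size is known only per child: 6.7 points on a term's incidence in an arm of 15, 3.3 at n=30 and 2.2 at n=45. In an arm of 15 that is enough to bring a term into the non-serious AE table. These figures assume the planned group sizes and no other treatment-emergent record of the same term in that child. The number of children affected cannot be estimated and is probably small.

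The primary endpoint and the sample size are untouched. It would go too far to conclude that the safety tables are unreliable or that split records cannot be traced. The defect is confined to one class of record, and the collected fields identify it.

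**What to change.** Add to SAP 10.2: *A record split from a pre-treatment adverse event is treatment-emergent only if its intensity is higher than the highest intensity of the parent event before the first dose.*

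Identify the pair by three conditions: same preferred term, parent outcome of not yet recovered, and parent outcome date and time equal to the onset of the second record. The adverse event log allows the time to be omitted, so match on date where no time is recorded. State that this rule takes precedence over the SAP 10.2 default that treats partially dated events as treatment-emergent.

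Optionally, limit the footnote in Protocol 8.2.2 to an increase in intensity after the first dose, so that an easing event stays one record with its original onset. This stops the problem at source, but the SAP sentence is sufficient without it and also covers records already split.

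The cost is one sentence in the SAP and a small matching step in the programming, with no new data. Genuine worsening is still counted.

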#### **Date and Time of Onset**

The date of onset is the date when the first sign(s) or symptom(s) were first noted. If the AE is an abnormal clinically significant laboratory test or outcome of an examination, the onset date is the date the sample was taken or the examination was performed.

# **Intensity**

The intensity of an AE must be classified using the following 3-point scale:

Mild: Awareness of signs or symptoms, but no disruption of usual activity

Moderate: Event sufficient to affect usual activity (disturbing)

Severe: Inability to work or perform usual activities (unacceptable)

# Causal Relationship to IMP

The possibility of whether the IMP caused the AE must be classified as one of the following:

# Reasonable possibility:

There is evidence or argument to suggest a causal relationship between the IMP and the AE. The AE may occur as part of the pharmacological action of the IMP or may be unpredictable in its occurrence.

# Examples:

- AEs that are uncommon but are known to be strongly associated with IMP exposure
- AEs that are not commonly associated with IMP exposure, but the event occurs in association
  with other factors strongly suggesting causation, such as a strong temporal association or the
  event recurs on rechallenge

## *No reasonable possibility:*

There is no reasonable evidence or argument to suggest a causal relationship between the IMP and the AE.

# Examples:

- known consequences of the underlying disease or condition under investigation
- AEs common in the trial population, which are also anticipated to occur with some frequency during the course of the trial, regardless of IMP exposure

Trial Code: 000103 Date: 28-Jul-2014 E-Protocol Amendment-18395; Ver. 5

> Supersedes: 4 Page 41 of 65

#### **Action Taken to IMP**

The action taken to the IMP in response to an AE must be classified as one of the following:

- No change (medication schedule maintained or no action taken)
- Withdrawn
- Interrupted
- Dose reduced
- Dose increased

#### **Other Action Taken**

Adverse events requiring therapy must be treated with recognized standards of medical care to protect the health and well-being of the subject. Appropriate resuscitation equipment and medicines must be available to ensure the best possible treatment of an emergency situation.

If medication is administered to treat the AE, this medication should be entered in the Concomitant Medication Log.

## **Date and Time of Outcome**

The date and time (time can be deleted/omitted, if applicable) the subject recovered or died.

# Outcome

The outcome of an AE must be classified as one of the following:

- Recovered (fully recovered or the condition has returned to the level observed at initiation of trial treatment)
- Recovered with sequelae (resulted in persistent or significant disability/incapacity)
- Recovering
- Not yet recovered
- Fatal

## 8.3 Pregnancy and Pregnancy Outcome

If a pregnancy occurs, the IMP should be immediately stopped and Pharmacovigilance at Ferring Pharmaceuticals must be informed. The mother and the fetus must be followed-up at least until the birth of the infant and 1 month after the birth of the infant. In general, the follow-up will include the course; duration, and the outcome of the pregnancy, as well as neonatal health. If a pregnancy results in an abnormal outcome (birth defect/congenital anomaly), this must be reported as an SAE to Pharmacovigilance at Ferring Pharmaceuticals.

Trial Code: 000103 Date: 28-Jul-2014 E-Protocol Amendment-18395; Ver. 5

Supersedes: 4 Page 42 of 65

In cases in which a fetus may have been exposed through transmission of the IMP via semen following paternal exposure, and the pregnancy results in an abnormal outcome (birth defect/congenital anomaly), this must be reported as an SAE to Pharmacovigilance at Ferring Pharmaceuticals.

# **8.4** Serious Adverse Events

# 8.4.1 Serious Adverse Event Definition

# Serious Adverse Events during the Trial

An event is defined a serious adverse event if it:	Guidance				
results in death	Any event resulting in a fatal outcome must be fully documented and reported, including deaths occurring within four weeks after the treatment ends and irrespective of the causal relationship to the IMP. The death of a subject enrolled in a trial is per se not an event, but an outcome.				
is life-threatening	The term life-threatening refers to an AE in which the subject was at immediate risk of death at the time of the event. It does not refer to an event, which may have caused death if it were more severe.				
requires in-patient hospitalization or prolongation of existing hospitalization	The term hospitalization means that the subject was admitted to hospital or that existing hospitalization was extended as a result of an event. Hospitalization describes a period of at least 24 hours. Over-night stay for observation, stay at emergency room or treatment on an out-patient basis do not constitute a hospitalization. However, medical judgment must always be exercised and when in doubt the case should be considered serious (i.e. if case fulfills the criterion for a medically important event). Hospitalizations for administrative or social purposes d not constitute an SAE. Hospital admissions and/or surgical operations planned befortrial inclusion are not considered AEs, if the illness or disease existed before the subject was enrolled in the trial, provided that the condition did not deteriorate durithe trial.				
results in persistent or significant disability/incapacity	Disability/incapacity means a substantial disruption of a person's ability to conduct normal life functions. In doubt, the decision should be left to medical judgment by the investigator.				
is a congenital anomaly/birth defect	Congenital anomaly/birth defect observed in any offspring of the subject conceived during treatment with the IMP.				
is an important medical event	Important medical events are events that may not be immediately life-threatening or result in death or hospitalization but may jeopardize the subject or may require intervention to prevent one of the other outcomes listed in the definition above. Examples of important medical events include AEs that suggest a significant hazard, contraindication or precaution, occurrence of malignancy or development of drug dependency or drug abuse. Medical and scientific judgment should be exercised in deciding whether events qualify as medically important.				
	Important medical events include any suspected transmission of an infectious agent via a medicinal product. Any organism virus or infectious particle (e.g. prion protein transmitting Transmissible Spongiform Encephalopathy), pathogenic or non-pathogenic, is considered an infectious agent. A transmission of an infectious agent may be suspected from clinical symptoms or laboratory findings indicating an infection in a subject exposed to a medicinal product.				

Trial Code: 000103 Date: 28-Jul-2014

E-Protocol Amendment-18395; Ver. 5 Supersedes: 4

Page 43 of 65

